5.12.4. Concomitant medical procedures

All medical procedures carried out from the first dose of the study drug to 30 days (including 30 days) after the last dose of the study drug should be recorded in source documents and eCRF of patients.

Surgical resection or palliative radiotherapy during the study treatment should be discussed with the sponsor before implementation. For patients who obtain PR, resection of residual lesions is allowed if patients have finished 12-month treatment. If the investigator considers the treatment meets the patient's best interests, after discussing with the sponsor, surgical resection or palliative radiotherapy can be carried out.

5.13. Other Precautions

To relieve potential risks of photostimulation/phototoxicity, patients should be instructed to take DCC-2618 (Ripretinib, ZL-2307), avoid strong sunlight, fluorescent lamp and other ultraviolet radiation sources during the study. For all patients who use DCC-2618 (ripretinib, ZL-2307), preventive skin care suggestions include use of SPF \geq 30 sunscreen cream, antiallergy moisturizer or ointment relieving dry skin, and mild skin care products containing tasteless soap and detergent.

Please refer to the approved package insert for warnings and precautions of sunitinib.

6. Study Evaluation

6.1. Screening

Screening must be carried out within 28 days prior to the first dose of the study drug to confirm that the patient meets inclusion criteria of the study. Radiographic examinations and dermatologic examinations can be carried out within 28 days prior to the first dose of the study drug. See Table 1 (Schedule of Assessments) for items to be assessed.

6.2. Re-screening

Patients can be re-screened only after obtaining the approval of the sponsor. If patients are rescreened, all screening evaluation items except tumor tissue specimens (if applicable) should be repeated. If radiographic evaluation, echocardiogram and dermatologic examination are carried out within 28 days prior to the first dose of the study drug, the examinations don't need to repeat. Patients can be re-screened once only. If patients are re-screened, screening time window will be timed after initiating the first re-screening evaluation item.

6.3. Treatment period

After confirming that patients meet all criteria, patients will be randomized to the study. The first dose of the study drug must be administered in department on C1D1. See Table 1 (Schedule of Assessments) for study visit schedule during treatment. Patients will be taken as outpatients during treatment. All visits should be carried out in the regulated window.

Patients who discontinue treatment with the study drug must return to the department for EOT visit within 7 days after the last dose of the study drug. If the interval between the last visit before discontinuing treatment with the invstigational drug and EOT visit is over 14 days (excluding 14 days), comprehensive evaluation of items should be carried out according to Table 1 (Schedule of Assessments) at EOT visit. If the interval between the last visit before discontinuing treatment with the invstigational drug and EOT visit is not more than 14 days (including 14 days), only items that are not evaluated at the last visit need to be assessed at EOT visit.

6.4. Follow-up

Patients will be contacted by telephone 30 (± 5) days after the last dose of the study drug for safety follow-up to evaluate AE, collect information of concomitant medications/other treatments and collect new information of anti-tumor therapy.

After that, patients will be contacted by telephone for OS follow-up to collect new information of anti-tumor therapy and OS data.

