Patients will receive treatment until progressive disease based on "RECIST v1.1-GIST-specific Criteria", intolerable adverse events or withdrawal of consent. If progressive disease is confirmed by the independent radiologic review using "RECIST v1.1-GIST-specific Criteria", patients who receive DCC-2618 or sunitinib will discontinue treatment with the study drug.

Table 1: Schedule of Assessments

Evaluation/Procedure ¹	Screening 2		Cycle 1		Сус	le 2	≥ Cycle 3	EOT visit	Safety follow- up	Overall survival
Cycle Day	-28 to -1	1 (Baseline)	15 (± 1 day)	29 (± 1 day)	1 (± 3 day)	29 (± 3 day)	1 (± 3 day)	(Within 7 days after the last dose)	Within 30 days after the last dose (± 5 day)	follow-up ³ (Every 2 month \pm 10 days)
Come to the Study Site	X	X	X	X	X	X	X	X		
Tel									X	X
Informed consent	X									
Inclusion/Exclusion criteria	X									
Previous medical history and tumor history	X									
Previous medications/treatment ⁴	X									
Pregnancy test ⁵	X	X*			X		X	X		
Hepatitis B/C tests ⁶	X						X	X		
HIV antibody test	X									
Clinical laboratory tests										
Blood routine	X	X*	X	X	X	X	X	X		
Blood biochemistry	X	X*	X	X	X	X	X	X		
Blood coagulation function ⁷	X	X*	X	X	X	X	X	X		
Urine routine ⁸	X	X*			X		X	X		
TSH, FT3 and FT4 ⁹	X	X*					X	X		
Physical examination	X	Examination will be arranged based on clinical findings and/or patients' chief complaints								
ECOG PS ¹⁰	X	X*	X	X	X	X	X	X		
Vital signs and weight ¹¹	X	X*	X	X	X	X	X	X		
Height	X									
12-lead ECG ¹²	X	X*			X		X	X		
Echocardiography/13	X						X	X		
Dermatologic examination ¹⁴	X						X	X		

Evaluation/Procedure ¹	Screening 2		Cycle 1		Cyc	le 2	≥ Cycle 3	EOT visit	Safety follow- up	Overall survival
Cycle Day	-28 to -1	1 (Baseline)	15 (± 1 day)	29 (± 1 day)	1 (± 3 day)	29 (± 3 day)	1 (± 3 day)	(Within 7 days after the last dose)	Within 30 days after the last dose (± 5 day)	follow-up³ (Every 2 month ± 10 days)
AEs reporting			Co	ntinuing from	m signing an l	CF to the saf	fety follow-up			
Concomitant medicines/other treatment				From t	he first dose o	f the study d	rug to safety follo	ow-up		
Administration of study drug ¹⁵		X	X	X	X	X	X			
Distribution and reconciliation of the study drug		X			X		X			
PK sampling ¹⁶		X	X		X		X			
Molecular test report, marking KIT/PDGFRA mutation status ¹⁷	X									
Archived tumor tissue sample/tumor biopsy ¹⁸	X									
Optional tumor biopsy 19								X		
Imageological examination ²⁰	X				X		X			
PD sampling (plasma) ²¹		X						X		

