7.9. Adverse Events of Special Interest (AESIs)

An AESI is an AE (serious or nonserious) of scientific and medical concern specific to study drug, for which ongoing monitoring and immediate notification by the Investigator to the Sponsor is required. Such AEs may require further investigation to characterize and understand them. AESIs may be added or removed during a study by a protocol amendment.

The following AEs are considered AESIs:

- Squamous cell carcinoma of skin
- Actinic keratosis
- Keratoacanthoma

7.10. **Adverse Events Reporting Period**

The AE (including SAEs and AESIs) reporting period begins from the time that the patient provides informed consent through and including 30 days after the last dose of the study drug, or until a new anti-tumor therapy is initated, which occurs first. For any SAEs or AESIs occurring after this reporting period, it will be reported only when a causal relationship between the SAEs or AESIs and study product is suspected by the study drug.

7.11. Adverse Event, Serious Adverse Event, and Adverse Event of Special Interest Reporting Requirements

Each patient must be carefully monitored for the development of any AEs. This information must be obtained in the form of non-leading questions (e.g. "How are you feeling?") and from signs and symptoms detected during each examination, observations of study personnel, and spontaneous reports from patients. All AEs (serious and non-serious) spontaneously reported by the patient and/or in response to an open question from study personnel or revealed by observation, physical examination or other diagnostic procedures must be recorded.

When possible, signs and symptoms indicating a common underlying pathology must be noted as 1 comprehensive event. Accompanying signs or symptoms (e.g. abnormal laboratory values) must not be reported as additional AEs. If a diagnosis is unknown, one or more symptoms may be reported as separate AEs. If an underlying diagnosis is subsequently determined for the reported symptom(s), then the reported symptom(s) term(s) must be revised to be "attributed" or "due" to the diagnosis.

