9.5.6.1. AEs

AEs in the safety population will be summarized with the number of events and proportion of patients according to system organ class (SOC) and preferred term. All tables will only include TEAE. "Treatment emergent" is defined as any AEs occurring during the first dose of the investigational drug and up to 30 days after the last dose of the investigational drug. However, the listing will include all AEs collected.

Toxicity grade of AE will be classified with NCI-CTCAE V5.0 (See Table 12). If a patient has the same SOC or preferred term evet for several times, only the most severe event will be summarized in the tables for that SOC and preferred term. AEs grade ≥ 3 will be summarized. Missing toxicity grade will not be imputed.

SAEs, AEs and AESIs that lead to dose reduction or discontinuation and AEs will be also analyzed.

Formal hypothesis test of incidence of AE will not be performed.

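### The safety follow-up call may be made from day 25, although adverse events are reportable and counted as treatment-emergent to day 30, so up to 5 days of the window can have no scheduled AE enquiry

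*Combined protocol and SAP*

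**What the plan says.** **Timing of the call.** Section 6.4 reads: "Patients will be contacted by telephone 30 (± 5) days after the last dose of the study drug for safety follow-up to evaluate AE". The synopsis and section 6.11.12 give the same 30 (± 5) days. Table 1 heads the column differently: "Within 30 days after the last dose (± 5 day".

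**AE window.** Section 7.10 runs reporting of AEs, SAEs and AESIs from consent "through and including 30 days after the last dose of the study drug, or until a new anti-tumor therapy is initated", whichever comes first. Section 9.5.6.1 defines treatment-emergent events as those from the first dose "up to 30 days after the last dose of the investigational drug". Sections 5.12.3 and 5.12.4 record concomitant treatments and medical procedures to day 30 inclusive.

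**Contacts around the call.** Under section 6.3, a patient who stops treatment "must return to the department for EOT visit within 7 days after the last dose of the study drug". The call is the next scheduled AE enquiry. Table 1 shows AE reporting as continuous from consent, but only as far as the safety follow-up, and its concomitant-treatment row ends at the same point. What comes later is set out in 6.4: "After that, patients will be contacted by telephone for OS follow-up to collect new information of anti-tumor therapy and OS data". Section 6.10.2 spaces these survival calls 2 months apart.

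**The concern.** The last scheduled question about AEs may be asked before the period it is meant to cover has ended. If the call is on day 25, the site has completed every scheduled safety contact, and Table 1 treats AE reporting as closed. Section 7.10 still has five days to run, and nothing in the protocol requires a second enquiry.

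Comparing the safety profiles of the two drugs is a secondary objective (2.2), and the incidence of TEAEs, SAEs and AESIs is a listed endpoint (9.2.2.2). The safety tables would present a window to day 30 that had not been actively observed to day 30 in every patient, and nothing in the tables would show it. Records of concomitant treatments and procedures would be cut short in the same way.

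**Working it through.** The plan gives no figure on this point to reproduce. The check is day arithmetic.

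**Inputs**
- Permitted call days: 30 ± 5, that is days 25 to 35, or 11 days (synopsis, 6.4, 6.11.12).
- End of AE reporting and of the TEAE window: day 30 (7.10, 9.5.6.1).
- Scheduled AE enquiries after the call: none (6.4, 6.10.2, Table 1).

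**Formula.** Days without scheduled enquiry = max(0, 30 − call day), taking a call to cover the day on which it is made.

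| Call day | Days not covered | Number |
|---|---|---|
| 25 | 26–30 | 5 |
| 26 | 27–30 | 4 |
| 27 | 28–30 | 3 |
| 28 | 29–30 | 2 |
| 29 | 30 | 1 |
| 30–35 | none | 0 |

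**Results**
- Worst case: 5/30 = 16.7% of the post-dose days.
- Permitted call days that leave a gap: 5 of 11.
- Average loss if calls were spread evenly over days 25 to 35: (5 + 4 + 3 + 2 + 1)/11 = 15/11 = 1.36 days per patient. The even spread is an assumption, since the documents give no distribution of call days.

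**Against the whole TEAE window.** That window starts at the first dose, so 30 days is only its tail. Assume treatment lasts about as long as the planning median PFS of 6 months (control) or 9 months (test), at 30.4 days a month:
- 6 months: 182.4 + 30 = 212.4 days, and 5/212.4 = 2.4%.
- 9 months: 273.6 + 30 = 303.6 days, and 5/303.6 = 1.6%.

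Even the worst case is therefore about 1.6% to 2.4% of the full TEAE window.

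**After the change.** With a window of 30 (+5) days the permitted call days are 30 to 35, which is 6 days, and the formula gives 0 for each of them.

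**The case against.** The call is not the only way an event can reach the database, and this largely stands.

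- Section 7.11 requires "spontaneous reports from patients" to be recorded, and 6.6 allows unscheduled safety assessments at any time.
- SAEs and AESIs within the reporting period must be reported within 24 hours of the investigator becoming aware of them, whatever the causality. Deaths within 30 days of the last dose have their own rule (7.11), and survival follow-up captures deaths in any case.
- Patients who stop treatment for reasons other than progression, death, withdrawal of consent or loss to follow-up continue imaging until progression or new therapy (6.10.1). It would be wrong to say that only survival contacts remain for everyone. These visits are not written as AE enquiries, however, and need not fall on days 26 to 30.
- Under 7.10, reporting stops when new anti-tumor therapy starts, so a patient who has already switched by the time of the call has no reporting gap. The TEAE definition in 9.5.6.1 lacks that cut-off, which is a separate mismatch and does not depend on when the call is made.

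These routes reduce the loss but do not remove it, because none of them schedules a question about AEs between an early call and day 30. The provision in 7.10 for later events does not fill the gap either. It begins only after the reporting period and covers only SAEs and AESIs with suspected causality.

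A reader might infer three stronger things that the documents do not support:
- That the timing biases the comparison between arms. The call rule is the same for both, nothing suggests that call days would differ, and AE incidence is not formally tested (9.5.6.1).
- That 17% of post-treatment events would be lost. The figure is a worst-case share of days, and no event rate is given for that interval.
- That late SAEs would commonly be missed. This would need the site never to learn of the event.

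**Conclusion.** The mismatch is real and small. A fully compliant call can leave 1 to 5 days of the stated AE window without scheduled enquiry in a patient called on days 25 to 29 who has not started new anti-tumor therapy. The data mainly at risk are non-serious AEs with onset on days 26 to 30, together with concomitant treatments and procedures on those days. TEAE incidence may be slightly understated. By how much cannot be computed, because the documents give neither the distribution of call days nor an event rate for those days.

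The Table 1 heading is a looser wording of the same rule. It should be aligned but is not separate evidence of a gap. The point is worth correcting because the correction is cheap. It does not threaten the safety conclusions.

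**What to change.** Change the call window from 30 (± 5) to 30 (+5) days after the last dose in the synopsis, 6.4, 6.11.12 and Table 1. Replace the opening words of the Table 1 column heading so that it gives the same window. Every permitted call then falls on or after day 30. The AE and concomitant-treatment rows of Table 1, which end at the safety follow-up, then no longer stop short of 7.10, 5.12.3 and 5.12.4.

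**Cost.** It is the same single call, made somewhat later for patients who would have been called on days 25 to 29. Permitted call days fall from 11 to 6, so there may be a few more out-of-window calls. A minor amendment is needed, with IRB/IEC approval under 10.2, which allows expedited review of minor changes where the regulator permits. If the sponsor prefers to keep the ± 5 tolerance, requiring a further AE enquiry at or after day 30 whenever the call was earlier would also close the gap, at the price of a second contact for those patients.

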6.5. Lost to Follow-up

Patients will be considered lost to follow-up in the following conditions: patients cannot be contacted by telephone three times within 2 weeks after the first failure of contact and telephone contact records should be made.

6.6. Study Evaluation

Table 1 Summarizes schedule of assessments of each visit.

Unless otherwise specified, all assessments must be carried out prior to administration and in the predetermined window of visit.

Additional unscheduled safety or efficacy assessment can be carried out at any time with clinical indications to confirm the correlation between the specific findings and the study drug and/or duration of the event.

6.7. Inform Consent Process

Each patient must sign and date the specific ICF before any specific procedure of the study. ICF will follow all applicable regulations of patient protection. The ICF approved by the sponsor, institutional review board (IRB) of the study site/independent ethics committee (IEC) must be used. The investigator or designated personnel must record consent process, including

recording the date of signing the informed consent form in source documents of patients.

6.8. Distribution of Patient Number

After obtaining informed consent, a unique patient identification number (patient number) will be assigned to each patient. Please refer to the study reference manual for details of assigning patient number. If the patient receives re-screening, a new patient number will be used.

6.9. Demographics and Medical History

Demographic information must be collected during screening.

Cancer history and prior treatment history (including reasons for treatment discontinuation) should be obtained during screening. Cancer history includes:

- Known GIST histological diagnostic
- Tumor mutation status: molecular test report of patients should be collected during screening and necessary archived and/or fresh tumor tissue samples should be collected. If the molecular test report provided by patients is available, randomization stratification can be carried out according to the molecular test report and it is not required to test archived tumor tissue samples or fresh live tissues before randomization. If patients cannot provide molecular test report or the report is unusable or insufficient, an archived tumor tissue sample or fresh live tissue should be tested to confirm KIT or PDGFRA mutation status prior to randomization. The central laboratory will analyze tumor tissues to identify mutation of KIT or PDGFRA.
- All prior anti-cancer therapy regimens, including:
 - Surgery (including tumor tissue samples): including date of resection surgery, site and range of resection (such as, resection of tumor tissue samples, R0, R1, or R2 only)
 - O Prior imatinib treatment: including treatment starting date, dose and dosing schedule, treatment reason (such as adjuvant therapy of metastatic disease), best response, progressive disease date, date and reasons of treatment discontinuation.
 - o Radiation therapy: including treatment site, total dose, treatment date and response
 - Other treatment procedures, such as radiofrequency ablation (if applicable)

Molecular test report with KIT/PDGFRA mutation status should be provided to the investigator before randomization. If molecular test report is unusable or insufficient, an archived tumor tissue sample or fresh live tissue should be tested to confirm mutation status prior to randomization.

The investigator must obtain medical history of each patient during screening, including any obvious adverse conditions and diseases during and before obtaining informed consent. It is necessary to evaluate whether patients have any unqualified medical conditions specified in the inclusion and exclusion criteria based on medical history assessment. Medical history

should include complete review of system, past medical history, surgery history and any allergy history. Ongoing signs of disease should be considered as comorbidities: if possible, starting date of these comorbidities should be recorded.

6.10. Effectiveness

6.10.1. Imageological examination

Enhanced pelvic, abdominal and chest CT scan of all patients will be carried out according to Table 1 (Schedule of Assessments) for tumor efficacy assessment. Radiographic examination prior to informed consent can be used for screening evaluation as long as the examination is performed within 28 days prior to the first dose of the study drug and meets requirements of the study.

Imageological examination can be performed within the corresponding study visit \pm 7 days during the study. After C7D1, based on the investigator's assessment, any initially indicated PR or CR should be confirmed \geq 4 weeks after start of response. MRI scans of the abdomen/pelvis and CT scan without contrast of the chest can be used for patients who are allergic to radiographic contrast media or at the Investigator's discretion based on the best interest of the patient after discussion with the Sponsor.For each patient, the same evaluation technology should be adopted during the whole study, and the evaluation technology could not be changed unless the investigator's consideration of safety risk. Ultrasound scan should not replace CT scan.

Copies of all imageological examinations must be obtained and sent to the independent imaging supplier designated by the sponsor. The independent imaging supplier will assess imaging quality and be responsible for institutional independent radiology review.

Independent imaging supplier must ensure institutional independent radiologic reviewers are blinded to investigator's assessment.

Independent radiologic reviewers and the investigator will evaluate tumor response using "RECIST v1.1-GIST-specific Criteria" (see Section Error! Reference source not found.). Response confirmed by investigators will be recorded in the eCRF. Assessment data obtained by the independent radiologic review (IRR) will be used for analysis of the primary endpoint.

Confirmation of progressive disease: If the independent radiologic reviewer confirms progressive disease using "RECIST v1.1-GIST-specific Criteria", the patient must discontinue the invstigational drug and receive EOT visit, safety follow-up, and OS follow-up.

Confirmation of absence of progressive disease: if institutional independent radiologic reviewers confirm there is no progressive disease, the patient will continue to receive the study drug, unless there are medical needs requiring discontinuation of the study drug (that is, rapid progression or clinical worsening). If investigators confirm progression according to clinical worsening, imageological examination should be performed and reviewed by institutional independent radiologic reviewers to confirm whether the patient has progression. Basis for

confirming progression based on clinical worsening should be recorded in source documents and eCRF of patients. If the investigator confirms progressive disease according to "RECIST v1.1-GIST-specific Criteria", the investigator should wait for assessment and confirmation by the independent radiologic review and then terminate the patient's treatment. If the investigator doesn't hope to confirm by the independent radiologic review or hopes to terminate the patient's treatment according to progressive disease based on "RECIST v1.1-GIST-specific Criteria" before obtaining results of the independent radiologic review, it is necessary to discuss with the sponsor.

Radiographic examination of patients of various treatment groups should be performed according to the predetermined time and cycle will not be influenced by suspension or delay of treatment with the study drug. If the patient discontinues treatment for reasons other than progressive disease, death, withdrawal of consent and lost to follow-up, the patient should receive radiographic examination for tumor assessment according to the specified time interval after treatment withdrawal until progressive disease based on "RECIST v1.1-GIST -specific Criteria" or initiation of new anti-tumor therapy.

